### **10.6 Post-Treatment Evaluation**

Subjects will return to the clinic site for a Post-Treatment evaluation 30 – 37 days after their last dose of study treatment.

The following assessments will be performed at that time

- Targeted physical examination (including weight) ([Section 16.3](#))

- Triplicate ECG obtained within 30 minutes of each other at least 3 minutes apart
- Vital signs
- Concomitant medications
- Adverse events, including SAEs
- Collection of clinical laboratory samples: blood samples for hematology and chemistry, urine samples for urinalysis
- Anti-Vicinium antibodies
- Blood or urine pregnancy test (WOCBP)
- The following are to be done if the subject has not discontinued treatment due to documented disease recurrence, progression and if they have not been performed within the past 8 weeks
  - Cystoscopy
  - Biopsy (directed). EpCAM determination by immunohistochemistry will be obtained on all positive biopsies.
  - Urine cytology

As described in **Section 15**, additional follow-up will occur for subjects with ongoing clinically significant AEs (e.g., those leading to study drug discontinuation) or SAEs assessed as related to study drug.

Subjects without a treatment failure (see **Section 14.2**) will continue to undergo evaluations for disease status (urine cytology, cystoscopy, directed biopsies) every 13 weeks until the sooner of a treatment failure or the determination of the 18-month event free survival analysis. Survival data also will be collected on subjects every 13 weeks. Once all subjects are no longer receiving study treatment and the 18-month event-free survival for the study is determined, the study will close and subjects will then be followed by their physician according to standard of care.

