**Table 4: Visit Schedule and Assessments (Maintenance Phase)**

Assessment	Maintenance Phase					Post-Treatment (30 – 37 days after last dose)
	Treatment Days	Every 2 Weeks	Every 4 Weeks	Every 13 Weeks	Between Weeks 23 and 27	
Cytology				X 		X 
Cystoscopy				X 		X 
Biopsy/TURBT				X 		X 
Physical examination			X 			X 
Triplett ECG						X
Vital signs	X 					X
Weight			X			X
Anti-Vicinium antibody test					X	X
Chemistry		X 				X
Hematology and urinalysis			X 			X
Urine or serum pregnancy test			X 			X
Concomitant medication	X 					X 
Adverse events (AEs / SAEs)	X 					X
Drug administration (once every other week)	X					
Contact to assess for progression and survival				X 		

 Window of 1 week before to 2 weeks after to start evaluation

 White-light cystoscopy. Any subject who underwent fluorescence cystoscopy for bladder biopsy/TURBT during the screening period must continue having this modality for all subsequent biopsies (however, white-light cystoscopy will suffice for all assessments if a biopsy is not required ([Section 14](#))).

 Directed biopsies of all areas suspicious for disease. Random biopsies are required if cystoscopy is negative and urine cytology is positive or there are two suspicious cytology results ([Section 14](#))

 Evaluation performed pre-dose and post-dose prior to leaving the clinic. Concomitant medications required post-dose only if additional medications (not including Vicinium) were administered during or after the start of the instillation

 Performed every 4 weeks during study participation in females of childbearing potential only.

 Evaluations performed if the subject has not discontinued treatment due to documented disease recurrence, progression and if they have not been performed within the past 8 weeks.

 Targeted physical examination.

 Additional follow-up will occur for subjects with ongoing clinically significant AEs (e.g., those leading to study drug discontinuation) or SAEs assessed as related to study drug.

 Urinalysis performed pre-dose if on a treatment day.

 Weeks 26, 39, 52, 65, 78, 91, 104

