 Starting after subject discontinues study drug. Progression will be assessed if the subject did not have disease progression as the reason for discontinuation of study drug and has not had a cystectomy.

 [Section 10.5.2](#).

 EpCAM and biomarker evaluation on all bladder biopsy/TURBT samples positive for urothelial carcinoma ([Section 16.7](#)).

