### **11.3 Study Withdrawal Criteria**

Subjects are free to withdraw from treatment or from any further participation in the study (i.e., withdraw consent) at any time and without prejudice to further treatment. The Investigator should discuss with the subject if they want to withdraw from further treatment only (i.e., additional data will be collected) or from all further study participation at which time no data will be collected for the subject. The investigator must withdraw a subject from all further study participation if that subject withdraws consent. No additional evaluations will be done or data collected for subjects who withdraw consent. All subjects withdrawing from further study treatment should have Post-Treatment evaluation 30 – 37 days after the last dose of study treatment and receive follow up disease evaluation (every 3 months ([Section 10.6](#)) and until a protocol-defined event as well as be contacted for data secondary endpoint (PFS, OS). The reasons and details relevant to subject withdrawal must be recorded in the case report form (CRF). The Investigator must notify the Medical Monitor if a subject is withdrawn from the study.

Subjects must be withdrawn from study drug for any of the following reasons:

- Withdrawal of informed consent
- Pregnancy ([Section 12.5](#))
- Treatment failure ([Section 14.2](#))
- Documented extravesical (i.e., upper or lower tract) urothelial carcinoma
- Development of a second malignancy that requires systemic therapy
- Cystectomy
- Unacceptable toxicity
- Persistent non-compliance with the protocol requirements
- Treating physician / study Investigator concludes that it would be in the subject's best interest
- Intercurrent illness that, in the judgment of the Investigator, may affect assessments of clinical status to a significant degree, and that requires discontinuation of study drug.
- Sponsor terminates the study.

Subjects may be considered withdrawn if they fail to return for visits, or become lost to follow-up for any other reason. Every attempt should be made to re-establish contact for subjects who are lost to follow-up (i.e., those subjects whose status is unclear because they fail to appear for study visits without stating an intention to withdraw). The Investigator should undertake appropriate due diligence and document steps taken to contact the subject (e.g., dates of telephone calls, registered letters).

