### **17.5 Analysis of Efficacy**

The primary efficacy analysis will be based on the complete response (CR) rate and duration of response in subjects in Cohort 1 (see [Section 10](#)). The number and percentage of subjects with CIS with or without papillary disease with a complete response will be summarized separately at each response assessment. Ninety-five percent (95%) confidence intervals around the complete response rate will be calculated using the Clopper-Pearson method. For subjects with CIS with or without papillary disease who achieve complete response, the duration of response, defined as the start of the complete response to the first documented case of treatment failure (see [Section 14.2](#)) or death, will be estimated using the method of Kaplan-Meier. Any subject who does not experience treatment failure or death will be censored at the last non-missing assessment.

All subjects will be included in the analysis of event-free survival (EFS). EFS will be estimated using the method of Kaplan-Meier. Protocol-defined events in the analysis of event-free survival are:

- Treatment failure (see [Section 14.2](#)). Subjects with a treatment failure that their post-Induction Phase assessment will be considered to have a treatment failure on study Day 1.
- Death (as a first event)

Subjects without evidence of a treatment failure who are diagnosed with upper or lower urinary tract urothelial carcinoma by histology, cytology or radiographic evidence as their first event will be censored in the analysis of EFS at the date of diagnosis.

Subjects without evidence of a treatment failure who undergo cystectomy will be censored in the analysis of EFS at the date of cystectomy.

Subjects who do not experience an event will be censored at the last non-missing assessment. Subjects with persistent disease during the Induction Phase (i.e., disease at the Post-Induction Phase evaluation) will be treated as having an event at Day 1. The ninety-five percent (95%) confidence

interval around the event-free survival rate at 18 months will be presented. Analyses of other time-to-event efficacy endpoints (time to cystectomy, time to disease recurrence, time to progression, progression-free survival, and overall survival) will be analyzed in a similar manner.

- Time to cystectomy: defined as the time from the date of first dose of study treatment to surgical bladder removal

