Progression-free survival (PFS) will be analyzed for subjects in Cohorts 1, 2 and 3 and is defined as the time from the date of first dose of study treatment to the date of disease progression (e.g., T2 or more advanced disease) or death on or prior to treatment discontinuation, whichever occurs first. Because disease assessments are not recorded after treatment discontinuation, a death after treatment discontinuation will not be counted as an event so as not to artificially inflate PFS. Subjects without disease progression or death will be censored at the last assessment.

Censoring rules for the analysis of PFS are presented in the table below.

Table: Censoring scheme for PFS in Cohorts 1, 2, and 3

Situation	Date of Event or Censoring	Outcome
Disease progression	Date of disease progression	Event
Death without disease progression and occurring prior to treatment discontinuation	Date of death	Event
Death without disease progression and occurring after treatment discontinuation	Date of last evaluable disease assessment on or prior to treatment discontinuation ^a	Censored ^a
No baseline disease assessment	Date of first dose	Censored
No on-study disease assessments and no death	Date of first dose	Censored
No disease progression and no death	Date of last evaluable disease assessment	Censored
New anti-cancer therapy received without treatment failure and reported prior to or on the same day as disease assessment	Date of last evaluable disease assessment on or prior to the date of initiation of subsequent therapy	Censored
Second non-NMIBC cancer reported prior to or on the same day as disease assessment	Date of last evaluable disease assessment on or prior to the date of diagnosis of non-NMIBC cancer	Censored
a This censoring rule acknowledges that disease assessments were not recorded after treatment discontinuation due to an AE.		

Overall Survival (OS)

Overall Survival (OS) is defined as the time from the date of first dose of study treatment to death due to any cause. Subjects who are alive will be censored at the date of last contact.

Fridericia Corrected QT (QTcF)

$$QTcF = \frac{QT}{\sqrt[3]{RR}}$$

Bazett Corrected QT (QTcB)

$$QTcB = \frac{QT}{\sqrt{RR}}$$

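### The SAP's PFS table counts progression found after drug is stopped but gives no follow-up for progression-free contacts, and its text leaves open whether off-drug progression counts at all

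*SAP*

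**What the plan says.** **Follow-up.** Protocol Table 4 has a 13-weekly row, "Contact to assess for progression and survival". Its footnote 11 starts this when study drug stops and adds: "Progression will be assessed if the subject did not have disease progression as the reason for discontinuation of study drug", unless the subject has had a cystectomy. SAP 1.3 repeats the row and the footnote. Protocol 11.3 says that subjects withdrawn from treatment are to "be contacted for data secondary endpoint (PFS, OS"). Protocol 10.6 says that subjects off drug without a treatment failure "will continue to undergo evaluations for disease status (urine cytology, cystoscopy, directed biopsies) every 13 weeks until the sooner of a treatment failure" or the 18-month event-free survival (EFS) analysis. After a treatment failure, no scheduled cystoscopy or cytology remains.

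**Analysis.** SAP 3.3.7 defines the PFS event as T2 or more advanced disease, or death, with a qualifier limiting events to the time up to stopping treatment. The stated reason is that disease assessments are not recorded after that. The text then says: "Subjects without disease progression or death will be censored at the last assessment". In the censoring table, the progression row is an event at its date with no on-treatment limit. Only the death rows are split at discontinuation. The row "No disease progression and no death" is censored at the last evaluable assessment of disease. OS and cystectomy-free days, by contrast, are censored at last contact, and the EFS text expressly includes long-term follow-up.

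**The concern.** A subject who stops drug for CIS, Ta or T1 disease has not had a PFS event and is still at risk of one. For that subject, the last evaluable assessment is about the failure visit. The table therefore keeps a failed subject in the risk set only if a later contact reports progression. A failed subject who stays progression-free through many contacts is removed at failure. Follow-up time then depends on the outcome, which Kaplan-Meier does not allow.

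The alternative is to apply the on-treatment qualifier to progression as well. Every non-progression failure is then censored at the moment when the risk of progression may rise, so the censoring is informative in the other direction.

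Two programmers could follow this text and produce quite different curves. SAP Section 12 tabulates PFS in four populations and six subgroupings, and SAP 7 mentions none of this.

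**Working it through.** **1. The plan's nearest figure.** No figure is given for PFS. Protocol 17.8 claims at least 80% power with 134 subjects for 18-month EFS of 20% against 30%. With n = 134, p0 = 0.20, p1 = 0.30 and two-sided alpha 0.05:

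Power = Φ{[(p1 − p0) − 1.96√(p0(1 − p0)/n)] / √(p1(1 − p1)/n)} = Φ{[0.100 − 1.96 × 0.0346] / 0.0396} = Φ(0.815) = 79.3%.

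That is close enough to treat 20–30% as the intended range.

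**2. How many subjects are affected.** Events by month 18 number 134 × 0.70 = 94 to 134 × 0.80 = 107. The few whose EFS event is itself T2 disease or death are settled at that point. For the rest, the contact is the only later source of progression status.

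**3. Direction, by hand (invented numbers).** Take 100 subjects. Sixty fail at Week 13 without T2 disease, and 40 stay failure-free and assessed to month 24. Of the 60, six report progression at the 12-month contact and 54 are progression-free at every contact.

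- Contacts used: 94/100 = 94%.
- Table taken literally: the 54 leave at Week 13, so 40 + 6 = 46 are at risk at month 12, and PFS = 1 − 6/46 = 87%.
- On-treatment progression only: no events, 100%.

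The literal rule errs downward whenever any off-drug progression is counted, whatever the rate.

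**4. Size, by simulation.** Assumptions not in the documents: 42% failure-free at Week 13, 22% at Week 78 and 18% at Week 104 (chosen near the Phase 2 response of 44% and the design EFS); 5% of failures are T2 at failure; no deaths, no cystectomy; all contacts made. PFS at 24 months:

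| Progression after failure, per year | Contacts used | Literal table | On-treatment only |
|---|---|---|---|
| 5% | 90.3% | 77.1% (−13.2) | 93.3% (+3.0) |
| 10% | 84.7% | 65.4% (−19.3) | 93.1% (+8.4) |
| 15% | 80.2% | 57.7% (−22.5) | 93.6% (+13.4) |

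The standard error of the first column at N = 134 is about 3 points. Re-runs gave literal-table errors of 12 to 19 points at 24 months and about 4 to 6 at 12 months.

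**5. Other assumptions.** A second model used 18-month EFS of 20% or 30%, 3-month response of 40% or 60%, death at 3% a year, progression at 3% a year before failure, and follow-up of 24–36 months. For 5–15% a year after failure:

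- The literal table is 2.0 to 6.3 points low at 12 months and 8.3 to 21.1 at 24 months.
- On-treatment counting is 1.8 to 12.2 points high at 24 months.
- If failure does not raise the risk (3% a year throughout; EFS 30%, response 40%), the literal table still gives 80.8% against a true 88.6%. On-treatment counting is then essentially right, at 88.7%.
- Counting all progressions and deaths, and censoring at last contact, recovers the true curve in every scenario.

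**6. Cystectomy.** Progression contact stops at cystectomy. With an assumed 30–50% a year having cystectomy after failure, the 24-month literal-table error in step 4 falls to about 7–9, 10–13 and 11–15 points.

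**The case against.** **The on-treatment reading may be the intended one.** The qualifier in the PFS sentence can govern progression as well as death, and an SAP that says no later assessments are recorded would not be expected to count later progressions. On that reading follow-up does not depend on the outcome. This stands as an ambiguity. It does not rescue the rule: the table limits only deaths, and censoring at failure carries its own upward error if failure raises the risk. The premise is also doubtful. The table's footnote ties it to discontinuation for an adverse event, and it conflicts with protocol 10.6, 11.3, 14 and Table 4, the SAP's long-term follow-up windows, and its post-treatment follow-up listing.

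**A contact might count as an assessment.** The PFS sentence alone allows this. The table row does not, and the SAP uses last contact elsewhere when it means it.

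**The protocol is not clear either.** Section 10 says that treatment failures are withdrawn from the study. Section 10.6 then mentions only survival data. Section 14 continues evaluations for PFS in subjects who stop for reasons other than progression, citing the treatment-failure section. These passages pull against Table 4 and 11.3. They blur what was to be collected, but the contact row, its footnote and 11.3 remain in force, and the SAP reproduces the first two.

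**The size is assumed.** This stands. The documents give no progression rate after failure, the largest errors are in the late tail, and cystectomy shrinks them.

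**Conclusion.** The concern holds as a defect in the PFS rule. Read literally, the table biases PFS down, and that direction needs no assumption about rates. Read with the on-treatment limit on progression, PFS is biased up if failure raises progression risk. On the design EFS figures, about 70–80% of subjects are affected by month 18. With assumed post-failure progression of 5–15% a year, the literal table is about 4–6 points low at 12 months and 12–22 at 24 months (8–21 in the second model; about 7–15 with frequent cystectomy). On-treatment counting is about 3–13 points high at 24 months.

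Three stronger readings are tempting and not supported:

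- That follow-up certainly depends on the outcome, so that the curve is wrong for most of the trial. This follows from one of two possible readings, and its size rests on rates that the documents do not give.
- That the SAP departs from the protocol's PFS. The protocol names PFS without defining it, and its own rule in 17.5 is similar: "Subjects who do not experience an event will be censored at the last non-missing assessment". The conflict is with the follow-up schedule.
- That the trial's main conclusion is at risk. PFS is a descriptive secondary endpoint with no power calculation or success threshold, and complete response is unaffected.

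This should be fixed, but it does not invalidate the plan.

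**What to change.** In SAP 3.3.7:

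1. Count progression whenever it is documented, on or off drug, and say so in both the text and the table.
2. Change the row "No disease progression and no death" to censor at the later of the last disease assessment and the last contact at which progression status was recorded.
3. Give the same follow-up to subjects who die after discontinuation: count the death, or at least do not censor back to before discontinuation. Changing rows 1 and 2 alone would leave 24-month PFS about 3–4 points too high (assuming 10% a year progression, 3–5% a year deaths and no cystectomy).
4. Add a PFS row for cystectomy, because progression contact stops there.
5. Keep the on-treatment version as a sensitivity analysis.

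If progression status from contacts was not captured in the database, label the endpoint as progression on study treatment and disclose the change in SAP 7.

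The cost is a few lines of SAP text and a different censoring-date variable. The downside is that progression reported at a contact is less rigorous than progression shown by cystoscopy or biopsy.

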3.3.8. By-Study Visit Displays

When data are collected serially over time, individual data presentations may include by-visit displays. Visits will be presented according to the nominal visit as obtained from the CRF or laboratory. If assessments are collected multiple times within a given visit, the value from the scheduled visit will be chosen over the value from the unscheduled visit. If there are two or more assessments with the same nominal visit label, the value closest to the nominal visit will be summarized. If two assessments have the exact same distance from the nominal visit by date and time, if applicable, then the last visit will be chosen for summarization. Unscheduled, End of Treatment, and Post Treatment Follow-Up Visits will be windowed according to visit date so that these data are appropriately analyzed. The following visit windows will be applied according to the following table:

Analysis Visit	Study Days	Target Study Day for Visit
Baseline	-8 < Study Day <= 1	
Week 1	1 < Study Day <= 7	1
Week 2	7 < Study Day <= 14	8
Week 3	14 < Study Day <= 21	15
Week 4	21 < Study Day <= 28	22
Week 5	28 < Study Day <= 35	29
Week 6	35 < Study Day <= 42	36
Week 7	42 < Study Day <= 49	43
Week 8	49 < Study Day <= 56	50
Week 9	56 < Study Day <= 63	57
Week 10	63 < Study Day <= 70	64
Week 11	70 < Study Day <= 77	71
Week 12	77 < Study Day <= 84	78
Week 13	84 < Study Day <= 91	85

Analysis Visit	Study Days	Target Study Day for Visit
Maintenance Month 1	91 < Study Day <= 121	115
Maintenance Month 2	121 < Study Day <= 152	146
Maintenance Month 3	152 < Study Day <= 182	176
Maintenance Month 4	182 < Study Day <= 212	206
Maintenance Month 5	212 < Study Day <= 243	237
Maintenance Month 6	243 < Study Day <= 273	267
Maintenance Month 7	273 < Study Day <= 303	297
Maintenance Month 8	303 < Study Day <= 334	328
Maintenance Month 9	334 < Study Day <= 364	358
Maintenance Month 10	364 < Study Day <= 394	388
Maintenance Month 11	394 < Study Day <= 425	419
Maintenance Month 12	425 < Study Day <= 455	449
Maintenance Month 13	455 < Study Day <= 485	479
Maintenance Month 14	485 < Study Day <= 516	510
Maintenance Month 15	516 < Study Day <= 546	540
Maintenance Month 16	546 < Study Day <= 576	570
Maintenance Month 17	576 < Study Day <= 607	601
Maintenance Month 18	607 < Study Day <= 637	631
Maintenance Month 19	637 < Study Day <= 667	661
Maintenance Month 20	667 < Study Day <= 698	692
Maintenance Month 21	698 < Study Day <= 773	722
Long-term Follow up Month 3	773 < Study Day <= 864	819
Long-term Follow up Month 6	864 < Study Day <= 955	910
Long-term Follow up Month 9	955 < Study Day <= 1046	1001

Analysis Visit	Study Days	Target Study Day for Visit
Long-term Follow up Month 12	1046 < Study Day <= 1137	1092
Long-term Follow up Month 15	1137 < Study Day <= 1228	1183
Long-term Follow up Month 18	1228 < Study Day <= 1319	1274
Long-term Follow up Month 21	1319 < Study Day <= 1410	1365
Long-term Follow up Month 24	1410 < Study Day <= 1501	1456

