### 10.4 Post-Induction Phase Evaluation

Subjects will be evaluated for disease status at the end of the Induction Phase. Urine cytology is obtained in week 12 as described above. Starting in week 13 (or as soon as possible after week 12) subjects will undergo cystoscopy and directed biopsies/TURBT of all lesions suspicious for disease. Subjects are eligible to receive Maintenance Phase treatment if they do not have a protocol defined treatment failure (see [Section 14.2](#)) or other criteria for study drug discontinuation (see [Section 14.3](#)) and are tolerating treatment.

See [Section 14.4](#) for criteria to continue treatment.

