5.3.3. Clinical Laboratory Assessments

Descriptive summaries of all quantitative clinical laboratory results will be presented by phase and visit, as appropriate. Laboratory abnormalities will be graded according to the NCI CTCAE version 4.03 grading system (http://evs.nci.nih.gov/ftp1/CTCAE/CTCAE_4.03_2010-06-14_QuickReference_5x7.pdf). The number and percentage of subjects experiencing treatment-emergent graded laboratory toxicities will be summarized. A laboratory abnormality is considered a treatment-emergent toxicity if it is an increase of 1 grade or more from the baseline toxicity value. Laboratory toxicity shifts from baseline to worst post-treatment toxicity will also be presented.

A spaghetti plot of clinical assessment by visit for subjects with a treatment emergent Grade 3 or higher lab abnormality. In addition scatter plots of lab values versus baseline will be produced for select labs by visit.

All clinical laboratory toxicities that occurred before the initiation of study drug will be excluded from the tables but will be included in the listings.

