5.3.4. Other Safety Analyses

Descriptive summaries of vital signs and their change from baseline will be presented by visit. The following values of vital signs will be considered potentially significant:

- Diastolic blood pressure
 - ≤ 55 mmHg and/or decrease of ≥ 20 mmHg from baseline

- ≥ 90 mmHg and/or increase of ≥ 30 mmHg from baseline
- Systolic blood pressure
 - ≤ 90 mmHg and/or decrease of ≥ 30 mmHg from baseline
 - ≥ 160 mmHg and/or increase of ≥ 40 mmHg from baseline
- Pulse
 - ≤ 50 bpm and/or decrease of ≥ 30 bpm from baseline
 - ≥ 120 bpm and/or increase of ≥ 30 bpm from baseline
- Temperature $> 38.3^{\circ}\text{C}$

The number and percentage of subjects with potentially significant vital signs will be summarized by visit.

Results from the triplicate 12-lead ECGs will be averaged and summarized by visit. Corrected QT values will be calculated using the Fridericia and Bazett corrections. The number and percentage of subjects with QTcF values > 470 msec for females and > 450 msec for males will be summarized by visit.

Medical history, physical examination findings, and pregnancy test results will be presented in the data listings.

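### SAP 3.3.8 files the off-drug Post-Treatment visit under Maintenance Month labels, which affects every scheduled ECG in those rows and the Maintenance Month 1 laboratory and vital-sign rows

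*SAP*

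**What the plan says.** SAP 3.3.8 presents visits under their nominal label but makes an exception: "Unscheduled, End of Treatment, and Post Treatment Follow-Up Visits will be windowed according to visit date so that these data are appropriately analyzed". The window table counts from first dose. After Week 13 it runs through Maintenance Month 1 ("91 < Study Day <= 121") to Maintenance Month 21, which ends on Day 773. Long-term follow-up rows start on Day 774. There is no End of Treatment or Post-Treatment row.

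Protocol 10.6 times the visit from the other end of treatment: "Subjects will return to the clinic site for a Post-Treatment evaluation 30 – 37 days after their last dose of study treatment". It collects chemistry, hematology, urinalysis, vital signs and a triplicate ECG. Protocol 11.3 applies it widely: "All subjects withdrawing from further study treatment should have Post-Treatment evaluation 30 – 37 days after the last dose of study treatment". Entry to maintenance is conditional (Protocol 10.4): "Subjects are eligible to receive Maintenance Phase treatment if they do not have a protocol defined treatment failure". A subject who fails the Week 13 evaluation therefore has the Post-Treatment visit without ever having maintenance.

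The displays that use these rows are in SAP 5.3.3 ("Descriptive summaries of all quantitative clinical laboratory results will be presented by phase and visit") and SAP 5.3.4 ("Results from the triplicate 12-lead ECGs will be averaged and summarized by visit"). SAP 5.3.4 also gives vital signs, and counts of QTcF above the sex-specific thresholds, by visit.

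**The concern.** A row labelled Maintenance Month should describe subjects in maintenance. Under this rule it also holds washout-period values, some from subjects who received induction only. A reader who compares Week 12 with Maintenance Month 1 could take a change in who is on drug for a change over time on drug. The ECG table could suggest that QTcF was observed during maintenance when no maintenance ECG is scheduled. The DSMB and 6-month outputs (Tables 8, 11 and 12 in SAP 10 and 11) are also by-visit tables, so the mislabelling would reach reviewers during the trial as well as in the final report.

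**Working it through.** The plan gives no figure to reproduce here. The check is date arithmetic, followed by the share of each row that is off drug.

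**1. Where the visit falls.** Visit day = last-dose day + 30 to 37.

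| Last dose | Post-Treatment visit | SAP 3.3.8 row |
|---|---|---|
| Week 12 (Days 78–84) | 78 + 30 = 108 to 84 + 37 = 121 | Maintenance Month 1 (Days 92–121) |
| Completer (Days 722–728) | 722 + 30 = 752 to 728 + 37 = 765 | Maintenance Month 21 (Days 699–773) |

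- Any last dose from Day 62 on puts the visit after Day 91 (62 + 30 = 92).
- The visit cannot reach a long-term row unless the last dose is on Day 737 or later (737 + 37 = 774).

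**2. ECGs.** Protocol Tables 3 and 4 schedule ECGs at Screening, Week 12 and Post-Treatment, with none in maintenance. The off-drug share of scheduled ECGs in maintenance rows is therefore 100%, whatever the failure rate.

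**3. Laboratory values and vital signs in Maintenance Month 1.** Let *s* be the share of subjects not failing after induction.
- Each of these contributes an on-drug value. Their own Post-Treatment visit cannot fall in this row, because a first maintenance dose on Day 92 gives Day 122 at the earliest.
- Each subject who fails contributes a Post-Treatment value, so the off-drug share is 1 − *s*.

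The documents do not give *s*, so it is ranged as an assumption. The low end is the 29% complete response in Phase 1 Tis subjects (Protocol 7). The simulation used 8,000 subjects per scenario, with sampling as in Protocol 10.5 and two rules for choosing among values in one window.

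| Assumed *s* | 1 − *s* | Simulated share, Month 1 |
|---|---|---|
| 75% | 25% | 25–26% |
| 60% | 40% | 39–41% |
| 40% | 60% | 59–60% |
| 29% | 71% | 70–72% |

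The other response rates in Protocol 7 fall inside this range: 39% (24/61, Phase 1) gives 61% off drug, and 44% (20/45, Phase 2) gives 56%.

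**4. Later rows.** During maintenance, chemistry is taken every 2 weeks, hematology every 4 weeks and vital signs at each dose. Each subject has one Post-Treatment visit. In the simulation, chemistry and vital signs in Months 2 to 21 were 0% to 16% off drug per row. Over all maintenance rows they were about 7% to 19% off drug. The within-window rule moved any row by no more than about 2 points.

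**5. ECG subjects without maintenance.** Each subject has one Post-Treatment ECG, so about 25% to 72% of scheduled ECGs in all maintenance rows together come from subjects who never had maintenance, over the same range of *s*.

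**The case against.** The strongest case for leaving the plan alone is that only descriptive by-visit displays are touched.
- Treatment-emergent laboratory toxicity counts a grade increase at any post-baseline assessment (SAP 3.3.7). Worst shifts use the worst value, whatever row it sits in (SAP 5.3.3). Neither depends on visit labels, and nor does the treatment-emergent adverse event definition.
- Protocol Table 4 shows openly that maintenance has no ECG, and dated ECG and dosing listings are planned.

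All of this stands and limits the point. It does not remove it, because the by-visit tables would still carry the wrong label.

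Four stronger readings are tempting, and the documents do not support them.
- A reader might infer that maintenance laboratory values and vital signs are mostly off drug throughout. They are not: on-drug sampling is frequent, and a majority is possible only in Month 1, and only if more than half of subjects fail after induction.
- A reader might turn the off-drug share into a dilution factor, so that at 44% response an on-drug laboratory change would appear at 44% of its size. That needs the effect to be wholly gone by 30 to 37 days, which no section states. It also carries a Phase 2 rate from CIS subjects on once-weekly dosing over to all subjects here. Maintenance chemistry is itself drawn at least 7 days after the prior dose, so the comparator is not a peak value.
- A reader might assume that the by-phase summaries fail in the same way. The SAP does not say that phase is derived from these windows.
- A reader might call maintenance the main new exposure. Phase 2 already included maintenance cycles, and twice-weekly induction is new too.

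**Conclusion.** The point holds in limited form. Followed as written, the rule mislabels every scheduled ECG in the maintenance rows and, with them, the QTcF threshold counts. It also mixes subjects who never had maintenance into Maintenance Month 1 laboratory values and vital signs, at about 25% to 72% of the row.

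The ECG result needs only the visit schedule. The Month 1 range rests on the assumed share not failing, on the last induction dose falling on Days 78–84, and on subjects attending the Post-Treatment visit. Dosing delays past Day 84 would move some visits into Month 2. Efficacy is not involved. The change is worth making before the by-visit tables are produced, but the point does not show that a laboratory safety signal would be missed.

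**What to change.** Add to SAP 3.3.8 an analysis visit, Post-Treatment (30–37 days after last dose), defined by days since last dose. Exclude those records from the Maintenance Month rows in Tables 14.3.4.1.1, 14.3.5 and 14.3.6 and in DSMB and 6-month Tables 8, 11 and 12.

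Do not restrict the maintenance rows to subjects with at least one maintenance dose. That would leave no row for Day 92–121 data from an eligible subject whose first maintenance dose is held, and those values should stay visible.

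The cost is one table row and a small programming change, in a window table that the SAP revision history shows was already edited in October 2020. Numbers in Maintenance Month 1 become smaller, and the maintenance ECG rows are empty apart from unscheduled tracings, which matches what was scheduled. No data are lost.
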